### 7.1.2.3 Criteria for Calculating the Apparent Terminal Elimination Half-Life

If the calculation of the apparent terminal elimination half-life is performed according to the non-compartmental analysis (NCA), then it will be based on PK nicotine concentration samples from days 4 and 5 and on the following rules.

t1/2 will be calculated according to the following formula:

$$t_{1/2} = \frac{\ln(2)}{\lambda_z}$$

where λz will be calculated by least squares (LS) linear regression of the terminal portion of the log-transformed plasma concentration-time curve.

The start of the terminal elimination phase for each subject will be defined by visual inspection and will be the first point at which there is no systematic deviation from the log-linear decline in plasma concentrations. The concentrations included in the terminal elimination phase will be flagged in the data listings.

#### Period of Estimation

- Apparent terminal (elimination) half-lives will be calculated, where possible, over at least 3 half-lives. Where an apparent terminal half-life is estimated over less than 3 half-lives, it will be flagged in the data listings.

#### Confidentiality Statement

- An apparent terminal half-life will not be reported if it can only be calculated over a period that is less than 1.5 half-lives.

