Plasma nicotine presents a biphasic profile, with a typical rapid initial disposition half-life ($t_{1/2a}$) of 1.35 hours, followed by a slower terminal elimination half-life ($t_{1/2z}$) of 17 hours (11). To ensure a full nicotine washout between each product use, a separation of 3 days would have been required ($\sim 5 \times$ elimination $t_{1/2z}$). Based on nicotine population PK modeling, it was estimated that subjects nicotine has entered in the terminal elimination phase with concentrations decreasing according to the terminal elimination rate constant (λ_z) after 8 to 10 hours post administration. As a consequence, a minimum of 10 hours have been established in this study design between the start of each use regimen to ensure appropriate washout of nicotine. Background-concentration correction will be applied to adjust for carry-over effects with adjustment of baseline values to the estimated $t_{1/2z}$ (or the terminal elimination rate constant λ_z) which will be derived from additional blood sampling on Day 5 for each subject.

The use of estrogen contraceptive is known to accelerate nicotine clearance by 20% to 30% compared to women who do not take oestrogen contraceptive (12). Therefore, for the purpose of this study, use of hormonal contraception containing estrogens is prohibited. This also applies to hormone replacement therapy.

The activity of CYP2A6 will be measured. CYP2A6 activity drives the metabolism of nicotine to cotinine and subsequent metabolites. Nicotine metabolism by CYP2A6 varies between individuals of the same ethnicity/race and across ethnicity/race due to genetic variations. These genetic differences could be associated with reduced/increased nicotine metabolism (8).

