7.5 Biomarker Assessment

7.5.1 Biomarkers of Exposure to Nicotine

For PK analysis of plasma nicotine levels, venous blood samples will be obtained according to the investigational site standard operating procedures (SOPs) at the following timepoints:

a) Fixed puffing (Morning: Days 1 through 4):

A total of 10 blood samples will be taken for fixed puffing PK parameter estimation. One blood sample will be taken prior to the product use (T_0 fix) 15 minutes \pm 5 minutes (T-1). Thereafter in relation to T_0 fix, blood will be drawn at the following time points: T1 after 2 minutes \pm 1 minute, T2 after 4 minutes \pm 1 minute, T3 after 7 minutes \pm 1 minute, T4 after 10 minutes \pm 1

Confidentiality Statement

Data and information contained in this document are considered to constitute trade secrets and confidential commercial information, and the legal protections provided to such trade secrets and confidential information are hereby claimed under the provisions of applicable law. No part of this document may be publicly disclosed without the written consent of Philip Morris Products S.A.

minute, T5 after 15 minutes \pm 2 minutes, T6 after 30 minutes \pm 2 minutes, T7 after 1 hour \pm 5 minutes, T8 after 2 hours \pm 5 minutes, and T9 after 4 hours \pm 5 minutes.

b) *Ad libitum* use (Afternoon: Days 1 through 4):

A total of 8 blood samples will be taken for the *ad libitum* PK parameter estimation. One blood sample will be taken prior to product use ($T_{0 \text{ ad lib}}$) at 15 minutes \pm 5 minutes (T-1). In relation to $T_{0 \text{ ad lib}}$, blood will be drawn at the following time points: T1 after 10 minutes \pm 1 minute, T2 after 20 minutes \pm 2 minutes, T3 after 30 minutes \pm 2 minutes, T4 after 40 minutes \pm 5 minutes and T5 after 1 hour \pm 5 minutes, T6 after 2 hours \pm 5 minutes, and T7 after 4 hours \pm 5 minutes.

c) Day of Discharge (Day 5)

A total of 5 blood samples will be taken on Day 5. Blood samples will be taken in relation to $T_{0 \text{ ad lib}}$ from Day 4 at the following time points: T1 after 14 hours \pm 30 minutes, T2 after 16 hours \pm 30 minutes, T3 after 18 hours \pm 30 minutes, T4 after 20 hours \pm 30 minutes and T5 after 24 hours \pm 30 minutes.

The actual collection time of each blood sample must be recorded on the CRF.

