12.5 Primary Objectives and Endpoints

12.5.1 Primary Endpoint Analysis Variables

PK endpoints are listed in section 3.1.

Nicotine PK parameters for fixed puffing regimen will be derived from plasma nicotine concentration versus time data using a non-compartmental analysis (NCA) technique using Phoenix WinNonlin, Version 7.0 or higher.

To minimize the carry-over effect in the nicotine plasma PK parameters due to limited washout periods (see Section 4.2), background-concentration correction will be applied to the concentration data for the fixed puffing regimen and *ad libitum* use. The baseline correction will be implemented by calculating the nicotine exposure parameters using adjusted concentration values as described below.

The nicotine terminal elimination rate constant λ_z (and $t_{1/2z}$) will be estimated from the Day 5 PK samples by using a linear regression on the log plasma nicotine concentration data. The regression analysis should contain data from at least 3 different time points in the terminal phase (including the last quantifiable concentration but excluding the concentration at t_{max}), consistent with the assessment of a straight line on the log- transformed scale. The nicotine plasma background-corrected PK parameters will be derived by performing the NCA on the corrected concentrations.

For the purposes of background-correction of the plasma concentrations post-baseline the following formula will be applied: $cC_t = C_t - C_0 \cdot e^{-\lambda_z t}$. Where, cC_t is the corrected concentration at each time point, C_t is the concentration at each time point, C_0 is the pre-use baseline concentration, λ_z is the Day 5 terminal elimination rate constant and t is the actual time.

The procedure of the baseline adjustment will be detailed in the SAP.

If plasma concentrations cannot be background-corrected in a sufficient number of subjects, alternative analysis methods will be used, as detailed in the SAP.

Confidentiality Statement

Data and information contained in this document are considered to constitute trade secrets and confidential commercial information, and the legal protections provided to such trade secrets and confidential information are hereby claimed under the provisions of applicable law. No part of this document may be publicly disclosed without the written consent of Philip Morris Products S.A.

In particular, the following PK parameters will be derived from nicotine levels adjusted for baseline:

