#### Confidentiality Statement

Data and information contained in this document are considered to constitute trade secrets and confidential commercial information, and the legal protections provided to such trade secrets and confidential information are hereby claimed under the provisions of applicable law. No part of this document may be publicly disclosed without the written consent of Philip Morris Products S.A.

Version	Date of Revision	Revision
Draft version 1.1	25APR2018	
[REDACTED] updated sections 7.1.2.3, 12.6.2.2.1, 13.1.3.1, 13.1.4 and 16.2 (Table 21) and the numbering of figures 15.1.4 as agreed with [REDACTED] and [REDACTED]
 
[REDACTED]
 
The update occurred prior to database lock but after the review of the draft results of the PK interim analysis
 
In section 7.1.2.3 it was clarified that the considerations regarding the period of estimation, the number of data points included into the calculation and the goodness of fit for apparent terminal elimination half-life can be applied only in case of non-compartmental analysis
 
In section 12.6.2.2.1 were added the new individual VAS craving result-time profiles
 
In section 13.1.3.1 it was clarified how to manage for the calculation of the PK parameters the background-corrected values that are below the bioanalytical LOQ threshold
 
In section 13.1.4 it was clarified which are the model-based estimated PK parameters whose geometric mean and CV% have to be presented
 
In section 16.2 (Table 21) and wherever applicable the numbering of figures was updated due to the insertion of the new individual VAS craving result-time profiles

Final version 2.0	30APR2018	[REDACTED] issued the final version 2.0 after Sponsor's approval

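### At the protocol's 17 h half-life the terminal-phase samples cannot meet the SAP's 1.5 half-life rule, and the gate that uses the rule could still keep NCA on a few subjects with biased λz

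*SAP*

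**What the plan says.** Protocol 4.2 describes biphasic decline, "followed by a slower terminal elimination half-life ($t_{1/2z}$) of 17 hours", and places entry into the terminal phase "after 8 to 10 hours post administration". Under protocol 7.5.1, "A total of 5 blood samples will be taken on Day 5": at 14, 16, 18, 20 and 24 h after the Day 4 ad libitum start, each ± 30 min. The last sample before these is at 4 h.

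Protocol 12.5.1 says that λz "will be estimated from the Day 5 PK samples by using a linear regression on the log plasma nicotine concentration data", using at least three terminal points. It sets no minimum span.

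SAP 7.1.2.3 widens the data for NCA: "it will be based on PK nicotine concentration samples from days 4 and 5". Visual inspection fixes the start of the phase at "the first point at which there is no systematic deviation from the log-linear decline in plasma concentrations". The section adds an adjusted R² of at least 0.700 and the span rule: "An apparent terminal half-life will not be reported if it can only be calculated over a period that is less than 1.5 half-lives".

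SAP 13.1.3.1 refers back to 7.1.2.3 to decide in how many subjects λz is reliable, and says that this limits who is evaluable for the background-corrected analysis. It moves to compartmental analysis (CA) when λz is not reliable in a relevant number of subjects, with 80% or more of the PK population as the example.

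**The concern.** The acceptance rule and the sampling scheme do not fit each other. The protocol's own half-life calls for more than twice the span that the Day 5 samples provide. The rule also sits in the section that decides whether the planned first method for cCmax, ctmax and cAUCfix can be used.

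The gate is unclear in a second way. Read literally, 80% is the share of subjects in whom λz must fail before CA is tried. The more natural intention is that λz should succeed in at least 80%. With visual selection of Day 4 samples, the literal reading could keep NCA for a minority of subjects, chosen partly because an early-phase point steepened their fit.

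**Working it through.** **Inputs from the documents.** Half-lives 1.35 h (initial) and 17 h (terminal); terminal onset 8-10 h; Day 5 samples at 14-24 h ± 30 min; last Day 4 sample at 4 h; minimum span 1.5 half-lives; adjusted R² ≥ 0.700; example threshold 80%; 18 randomized. The plan states no required span in hours, so there is no figure to reproduce.

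**Assumptions.** The documents give no between-subject spread, residual error or coefficient ratio. Every CV and ratio below is assumed and shown as a range.

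**Span.** Required: 1.5 × 17 = 25.5 h. The longest half-life that can pass is span / 1.5.

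| Samples used | Span | Half-lives at 17 h | Longest passing half-life |
|---|---|---|---|
| 14 to 24 h | 10 h | 10/17 = 0.59 | 6.7 h |
| 13.5 to 24.5 h | 11 h | 11/17 = 0.65 | 7.3 h |
| 4 to 24 h | 20 h | 20/17 = 1.18 | 13.3 h |
| T0 ad lib to 24.5 h | 24.5 h | 24.5/17 = 1.44 | 16.3 h |

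**Day 5 points only, log-normal half-life, median 17 h.** The pass probability is Φ[ln((span/1.5)/17) / √ln(1+CV²)]. At between-subject CV 20/30/50/80% it is 0/0.07/2.4/9.2% for a 10 h span and 0/0.2/3.8/11.6% for 11 h. At most 18 × 0.116 = 2.1 of 18 subjects are expected to pass.

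**Gate.** 0.80 × 18 = 14.4, so the threshold is 15 subjects. If at least 15 must succeed, the chance of keeping NCA on these points is effectively zero. If at least 15 must fail before CA is tried, NCA survives with only 4 passing.

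**The fit rule alone.** Simulated five-point Day 5 fits at a true 17 h, requiring adjusted R² ≥ 0.700 and a negative slope:

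| Residual CV | 3% | 5% | 8% | 10% | 15% |
|---|---|---|---|---|---|
| Fits accepted | 100% | 98% | 73% | 56% | 31% |
| P(at least 15 of 18 accepted) | 1.00 | 0.999 | 0.25 | 0.015 | 0.000 |

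Clean data pass this rule and are stopped by span. At about 8-10% noise or more, the fit rule would usually fail the gate by itself.

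**Admitting the 4 h sample.** The span rule applies to the fitted half-life. With half-lives of 1.35 and 17 h and an initial-to-terminal coefficient ratio of 2, the 4 h point lies 30% above the Day 5 line. Without noise, including it gives a fitted half-life of 12.7 h and a span of 20/12.7 = 1.57 half-lives, which passes. Extrapolating the Day 5 line to 4 h (mean time 18.4 h, sum of squares 59.2) has a prediction standard error of √(1 + 1/5 + 14.4²/59.2) = 2.17 residual SDs. At residual CV 10% the offset is therefore ln 1.30 / (2.17 × 0.10) = 1.2 standard errors, which is hard to see by eye.

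As a stand-in for visual inspection, the next simulation keeps the 4 h point when it lies within two prediction standard errors, then applies the span and R² rules (ratio 2):

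| Residual CV | 5% | 8% | 10% |
|---|---|---|---|
| Pass, no between-subject spread | 27% | 47% | 51% |
| P(at least 15 of 18 fail) | 0.24 | 0.008 | 0.003 |
| Pass, between-subject CV 30% | 19% | 39% | 45% |
| P(at least 15 of 18 fail) | 0.57 | 0.04 | 0.01 |

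That is roughly 3 to 9 of 18 subjects (18 × 0.19 = 3.4; 18 × 0.51 = 9.2). The chance that 15 or more pass is at most 0.005. At ratio 4 and residual CV 5%, nearly all subjects still fail.

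**Effect on the correction.** The subtracted 0-4 h area is C0(1 − e^(−4λ))/λ, with λ = ln 2 / half-life. It is 3.41, 3.69 and 3.84 × C0 at 8.5, 17 and 34 h, so relative to 17 h it changes by about −8% and +4%.

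**The case against.** The best defence has four parts.

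- **Reporting is not use.** The span rule governs whether a half-life is reported, while the R² rule governs whether it is calculated. The SAP never says that an unreported half-life removes λz from the correction. This stands, and the point is conditional on it.
- **Failure is a planned branch.** Protocol 12.5.1 and 12.7 foresee that λz may not be estimable, and testing this is the purpose of the interim PK analysis. CA waives the span, point-count and fit criteria. Population PK and uncorrected parameters follow. The 80% is only an example, and the method choice rests on an interim report reviewed by the sponsor. This also stands and limits the consequence.
- **The SAP uses Days 4 and 5, not Day 5 alone.** This is right. A reader might infer from 25.5 h against 10 h that NCA must fail on any reading of the gate, with 0 to 2 of 18 subjects passing, and that span rather than data quality is the whole cause. The documents do not support that. An accepted 4 h point can carry a subject past the rule, the literal threshold tolerates many failures, and the R² rule is a second obstacle at moderate noise. The defence does not rescue the plan, because the 4 h sample precedes the protocol's own 8-10 h onset and such passes rest on a λz that is too steep.
- **The numerical effect is small.** This is correct for the subtracted area and argues against a high severity.

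**Conclusion.** The mismatch is real. At 17 h the rule needs 25.5 h and the terminal-phase samples give 10 to 11 h, so essentially no subject with a half-life near 17 h can qualify on them. If an unreported half-life means no usable λz, the reading that requires at least 80% success is expected to fail whatever the data quality. Under the literal wording the outcome is uncertain: NCA could be retained with roughly 3 to 9 of 18 evaluable subjects and biased λz, depending on the assumed ratio, noise and way of judging the 4 h point.

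It would be too strong to infer that the primary results are compromised. Fallbacks are prespecified, uncorrected parameters need no λz, and the correction is insensitive to it. The 17 h figure is one typical value without a stated spread. What is at risk is a meaningful test of the simplest method and a clear rule for leaving it. Severity is minor to moderate. Confidence is high for the arithmetic and lower for the pass rates with Day 4 data.

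**What to change.** 1. In SAP 13.1.3.1, restate the gate: if λz is reliably estimated in fewer than 80% of the PK population (fewer than 15 of 18), evaluate CA.
2. In SAP 7.1.2.3, exclude samples taken before the stated 8-10 h terminal onset from the λz regression. In practice this removes the 4 h sample and returns to the protocol's Day 5 fit.
3. State whether the span rule bars use of λz for background correction. If it does, acknowledge that Day 5 sampling cannot meet it at 17 h and that CA is the expected method. If it does not, make span a flag for correction and define reliable as at least three points, a negative slope and adjusted R² ≥ 0.700.
4. The SAP revision history says of the v2.0 changes: "The update occurred prior to database lock but after the review of the draft results of the PK interim analysis". Document this change as made after that review, and report λz acceptance counts under both the current and the amended rule.

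No new samples or subjects are needed. Items 1 and 2 are cheap. The second option in item 3 is a trade-off, since it loosens a method-selection rule after interim review and leaves individual λz values imprecise. The R² filter also favours steep fits: at a true 17 h the median accepted half-life is 16.9/16.0/15.0/12.7 h at residual CV 5/8/10/15%, which moves the subtracted area by 0.0/−0.5/−1.0/−2.7%. CA stays likely at residual CV of about 8-10% or more.

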#### Number of Data Points

- At least 3 data points in the terminal phase with nicotine concentration greater than the LLOQ will be used for each subject in the regression analysis. An apparent terminal half-life will not be reported if derived from less than 3 data points. All available data points that are consistent with the assessment of a straight line on the log-transformed scale will be considered and always including the last quantifiable concentration but excluding the concentration at  $t_{max}$ .

#### Goodness of Fit

- When assessing apparent terminal phases, the coefficient of determination,  $R^2$  adjusted value, will be used as a measure of the goodness of fit of the data points to the determined line. This parameter will be used as it is considered to be a better assessment of the goodness of fit, compared to  $R^2$ , as it adjusts for the number of points included in the line therefore allowing for a more direct comparison between elimination phases determined using different numbers of data points.
- Apparent terminal half-life will only be calculated if the  $R^2$  adjusted value of the regression line is greater than or equal to 0.700.

If the calculation of apparent terminal elimination half-life is performed according to the compartmental analysis (CA), then it will be based on PK nicotine concentration samples from days 1 to 5 and all the considerations regarding the period of estimation, the number of data points included into the calculation and the goodness of fit will be no more applicable.

### **7.1.3 Anomalous Values**

During the pre-analysis data review, nicotine concentration values will be reviewed for their inclusion in the analysis. If a concentration value is considered to be anomalous due to being inconsistent with the expected PK profile it will be flagged in the listings and if applicable in the figures.

Exclusion of abnormal concentrations (i.e. sudden increases or drops in concentration, inconsistent with a typical plasma nicotine PK profile) will be avoided, hence outlier values may only be excluded in the event there exists an explanation that clearly justifies such exclusion (e.g. protocol violation, documented sample handling errors, interruption of product use during fixed regimen, and/or analytical errors, best scientific judgment).

The reason for the exclusion of abnormal concentrations (if any) will be documented. If the exclusion has a meaningful impact on the overall interpretation of the results, then it will also be discussed between Certara and PMI and fully documented.

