#### **Confidentiality Statement**

Data and information contained in this document are considered to constitute trade secrets and confidential commercial information, and the legal protections provided to such trade secrets and confidential information are hereby claimed under the provisions of applicable law. No part of this document may be publicly disclosed without the written consent of Philip Morris Products S.A.

This report will include a discussion on the evaluated background-correction methods and Certara recommendation as the best method to be taken for the final PK analysis following database lock. In addition, it will describe the results and provide Tables, Figures and Listings related to interim PK concentrations and/or parameters.

All the unadjusted PK parameters will be calculated for the interim analysis as described in Section 7.1.2 "PK Parameters".

The interim analysis report, will include the following figures:

- Individual and geometric mean (CV%) plasma nicotine concentration versus time profiles by product variant and product use regimen (linear and semi-log scales)
- Boxplots of PK exposure parameters (e.g.  $C_{max}$ , AUC) by product variant and product use regimen (fixed and ad libitum)
- Compartmental method only:
  - Goodness-of-fit/Diagnostic Plots
  - Individual PK model fits

The following summaries will also be provided:

- Geometric mean (CV%) unadjusted PK parameters for fixed and ad libitum regimens
  - Note: The background-corrected parameters will not be estimated during interim evaluations.
- Number of subjects with robustly estimated  $\lambda_z$  (or  $t_{1/2z}$ ) for each of the evaluated background-correction methods (including the number of subjects for which  $\lambda_z$  could not be reliably estimated).
- For the compartmental method only (provided this method is evaluated and that there is sufficient data to apply a model-based approach):
  - Geometric mean (CV%) model-based estimated PK parameters (e.g. volume of distribution, clearance).

The following listings will also be provided:

- Listing of NCA-derived individual PK parameters
- Listing of the model compartmental analysis individual parameters (only if this methodology is evaluated).
- List of data excluded or imputed in the analysis

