## 13.5 Final Analyses

Final analyses for this study will be performed only after database lock. A pre-analysis data review meeting will be held prior to database lock and completion of the final analyses. In addition, no database may be locked, or analyses completed until the final version of this SAP has been approved.

Any post-hoc, additional exploratory analyses completed to support planned study analyses, which were not identified in this SAP, will be documented and reported as applicable. Any results from these unplanned analyses will also be clearly identified in the text of the CSR.

The list of all tables, figures and listings to be presented are included in the relevant sections of the SAP.

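### SAP 7.1.3 lets nicotine concentrations be excluded on scientific judgment alone, at a review held after interim results by variant, with no analysis planned that keeps all values

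*SAP*

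**What the plan says.** **The exclusion rule.** SAP 7.1.3 (Anomalous Values) states that excluding abnormal concentrations is to be avoided and that "outlier values may only be excluded in the event there exists an explanation that clearly justifies such exclusion". The examples in brackets are mostly events that leave a trace: a protocol violation, a documented handling error, interrupted use in the fixed regimen, an assay error. The list closes with "and/or analytical errors, best scientific judgment".

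**The safeguards.** The same section flags anomalous values in the listings and, where applicable, the figures. It also says "The reason for the exclusion of abnormal concentrations (if any) will be documented". A further step, in which the PK vendor and the sponsor discuss the exclusion and record it in full, has this trigger: "If the exclusion has a meaningful impact on the overall interpretation of the results".

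**When it happens.** SAP 7.1.3 says "During the pre-analysis data review, nicotine concentration values will be reviewed for their inclusion in the analysis". SAP 13.5 says "A pre-analysis data review meeting will be held prior to database lock and completion of the final analyses".

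**What has been shown by then.** SAP 13.1.4 specifies an interim report, reviewed by the sponsor, that contains "Boxplots of PK exposure parameters" by variant and regimen, concentration profiles by variant and regimen, and all unadjusted PK parameters. Background-corrected parameters are not estimated at that stage. The revision history (SAP 3.1) records that the changes leading to version 2.0 were made before database lock but after the draft interim results had been reviewed.

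**Sensitivity analyses.** The only sensitivity analyses planned for the PK parameters (SAP 12.6.1 and 12.6.2.1) restrict the data to P3P 1, 2 and 4 on Days 2 to 4 and concern the study-day term.

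**The concern.** A rule that demands a justifying explanation, and then accepts judgment as one, does not restrict much. The other grounds can be checked against a record by someone who does not know what the exclusion does to the results. Judgment cannot be checked in that way. It also has little to rest on: the benchmark in SAP 7.1.3 is consistency with the expected profile, and protocol 2.1.2 says there are no human data on nicotine absorption from this product.

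The order of events adds to this. The review comes after a report that displays exposure by variant, in an open-label study, and no review without variant labels is specified. The discussion of influential exclusions is triggered by their effect on interpretation, so that effect is known when the discussion takes place.

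Cmax is the most exposed endpoint. SAP 7.1.2.1 reads it directly from the profile, so it is a single sample, and excluding that sample replaces a primary value with the next highest. Uncorrected Cmax and AUC are primary endpoints alongside the corrected ones, and both forms use the same samples.

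**Working it through.** **Inputs from the documents**
- 6 sequences × 3 subjects = 18 randomized, which reproduces the planned figure (protocol 12.2, SAP 8).
- Nine post-use samples per subject per fixed-regimen session (protocol 7.5.1), so 18 × 9 = 162 per variant.
- Model for log Cmax and log AUC: sequence, variant, dummies for Day 3 and Day 4, random subject (SAP 12.6.1). P3P 3 is always used on Day 1.
- At least 8 subjects of each sex (SAP 6.3.1), with ratios also presented by sex (SAP 12.6.1).

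**Assumptions, because the documents give no figures**
- Ratio r of the excluded peak to the next highest value: 1.5 to 3.
- Within-subject CV: 30%. Complete data on all 18 subjects.

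**Step 1. Geometric mean of one variant.** On the log scale one subject has weight 1/18, so k exclusions lower the mean by 1 − r^(−k/18).

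| r | k = 1 | k = 2 | k = 3 |
|---|---|---|---|
| 1.5 | 2.2% | 4.4% | 6.5% |
| 2 | 3.8% | 7.4% | 10.9% |
| 3 | 5.9% | 11.5% | 16.7% |

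In a stratum of 8, one exclusion gives 1 − r^(−1/8) = 4.9% to 12.8%.

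**Step 2. Ratios P3P 2 vs P3P 1 and P3P 2 vs P3P 4.** These contrasts are balanced over Days 2 to 4, so every observation on the two variants has weight ±1/18. The one-exclusion figures in Step 1 carry over. The ratio falls if the exclusion is on P3P 2 and rises if it is on the comparator.

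**Step 3. Ratio P3P 2 vs P3P 3.** Day 1 and Day 2 share a reference level, so the estimate is

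mean(P3P 2) − mean(P3P 3) − [mean(Day 3) + mean(Day 4) − 2 × mean(Day 2)] / 3.

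The weight of a P3P 2 value is therefore
- on Day 2: (1 + 2/3)/18 = 1.67/18, so the shift is 1 − r^(−1.67/18) = 3.7% to 9.7%;
- on Day 3 or 4: (1 − 1/3)/18 = 0.67/18, so the shift is 1 − r^(−0.67/18) = 1.5% to 4.0%.

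**Step 4. Scale against the confidence interval.** With CV 30%, σ = √ln(1 + 0.30²) = 0.294. Residual degrees of freedom are 72 − 18 − 5 = 49, so t = 2.01.
- P3P 2 vs P3P 1 or P3P 4: SE = σ√(2/18) = 0.098, and the 95% CI is the ratio ×/÷ exp(2.01 × 0.098) = 1.22.
- P3P 2 vs P3P 3: the squared weights sum to 48/324, so SE = σ√(48/324) = 0.113 and the factor is 1.25.

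To move a P3P 2 vs P3P 1 ratio by the full factor of 1.22 would take k = 18 × ln(1.22)/ln(r) same-direction exclusions: about 8.8, 5.2 or 3.3 for r = 1.5, 2 or 3.

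**Step 5. AUC.** The check used an assumed profile: peak of 10 ng/mL at 7 minutes, then an 85/15 biphasic decline with the protocol's half-lives of 1.35 and 17 hours. One post-use sample other than the 4-hour sample was taken as 1.5 to 2 times too high. Excluding it changes that subject's AUC by about −0.2% (2-minute sample) to −21% (2-hour sample). On the geometric mean of 18 that is at most 1 − 0.79^(1/18) = 1.3%. A single exclusion matters less for AUC than for Cmax.

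**The case against.** The strongest reply is that the judgment item is a loose ending to a list of examples inside a restrictive rule. Exclusion is to be avoided, the justification test still governs, the reason is written down, and anomalous values are flagged. SAP 13.1.4 also requires a list of excluded or imputed data in the interim report, and individual uncorrected concentrations are listed in the final outputs. This stands, and it defeats the reading that values could disappear without a stated reason. What remains is that judgment is itself an acceptable reason.

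Other stronger readings also go beyond the documents:

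- **That the people who saw the interim results decide the exclusions.** The SAP does not name the reviewers. Overlap is inferred from the PK vendor and the sponsor appearing at both steps. Because the study is open label, people handling subject-level data could know the variant in any case.
- **That the rule was loosened after the interim.** The revision history does not list 7.1.3 among the sections changed.
- **That the interim had no use for variant information.** The compartmental fallback (SAP 13.1.3.2) builds its surrogate dose from the 1 or 2 mg capsule content, so the modeller must know which uses were 1 mg. Choosing a correction method does not need exposure boxplots by variant, but restricting the report now would achieve little, since draft results have been reviewed.
- **That the review should also hide study day.** Deviations, interrupted use and carry-over must be matched to a specific day.

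Finally, no hypothesis is tested and SAP 12.1.8 says no claim rests on individual intervals. That limits the consequence to biased descriptive estimates.

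**Conclusion.** The point holds as a minor one. SAP 7.1.3 contains an exclusion ground with no criterion, applied at a review that follows interim results by variant, and no planned analysis shows what the exclusions did. The safeguards make exclusions traceable. They do not show the reader the ratios with all values retained. Deciding whether an exclusion is influential implies some comparison, but the SAP neither specifies nor tabulates one.

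The sizes rest on the assumed peak ratio of 1.5 to 3 and CV of 30%. One exclusion is small beside a confidence interval factor of 1.22 or 1.25. Two or three in the same direction on one variant, or one in a by-sex table, would be noticeable. The documents show openness to result-driven exclusion; they do not show that any took place.

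**What to change.** 1. In SAP 7.1.3, delete best scientific judgment from the list, so that exclusion requires a documented cause at the level of the sample, the assay or the product use.
2. State that if any concentration is excluded, the Cmax and AUC models will be rerun with all values retained and both sets of ratios reported.
3. Where practicable, make the first pass of the concentration review on listings without variant labels, keeping study day.

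Under version 2.0 the review and database lock are still ahead, so all three can be adopted. The cost is a wording change, one listing, and a rerun of existing models only if something is excluded. The downside is that an implausible value with no documented cause stays in the main analysis. It can still be flagged, as the SAP already provides.
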